20.2 Data Submission and Security Plan

20.3 Subject Enrollment

20.4 Reporting of Adverse Events and New Information

20.5 Audit and Monitoring Plans

21.0 Adverse Event Reporting

21.1 Reporting Adverse Reactions and Unanticipated Problems to the Responsible IRB

In accordance with applicable policies of The Pennsylvania State University Institutional Review Board (IRB), the investigator will report, to the IRB, any observed or reported harm (adverse event) experienced by a subject or other individual, which in the opinion of the investigator is determined to be (1) unexpected; and (2) probably related to the research procedures. Harms (adverse events) will be submitted to the IRB in accordance with the IRB policies and procedures.

21.2 Auditing and Inspecting

The investigator will permit study-related monitoring, audits, and inspections by the Penn State quality assurance program office(s), IRB, the sponsor, and government regulatory bodies, of all study related documents (e.g., source documents, regulatory documents, data collection instruments, study data etc.). The investigator will ensure the capability for inspections of applicable study-related facilities (e.g., pharmacy, diagnostic laboratory, etc.).

22.0 Study Monitoring, Auditing and Inspecting

22.1 Auditing and Inspecting

The investigator will permit study-related monitoring, audits, and inspections by the Penn State quality assurance program office(s), IRB, the sponsor, and government regulatory bodies, of all study related documents (e.g., source documents, regulatory documents, data collection instruments, study data etc.). The investigator will ensure the capability for inspections of applicable study-related facilities (e.g., pharmacy, diagnostic laboratory, etc.).

24.0 Appendix

24.1 Test Article(s) (Study Drug(s) and/or Study Device(s))

24.1.1 Description

Prazosin is an FDA approved medication indicated for the treatment of hypertension. A common off-label use of the medication is PTSD-related nightmares and sleep disruptions. Prazosin is supplied in capsule form.

24.1.2 Treatment Regimen

In this study, prazosin capsules and placebo capsules will be used for 3 weeks each. Capsules are taken by mouth at bedtime. The starting dose will be 1 mg and titrated by 1-2 mg each week as needed to achieve maximum therapeutic benefit while monitoring any adverse effects.

24.1.3 Method for Assigning Subject to Treatment Groups

All subjects will receive prazosin and placebo as a treatment at separate intervals during the study. The randomization process will determine which subjects receive prazosin first and which subjects will receive placebo first. We will use computer generated random numbers for randomization process.

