1.0 Objectives

1.1 Study Objectives

The aim of our study is to evaluate the effectiveness of prazosin in bulimic patients experiencing distressing nightmares secondary to PTSD. We will be testing 10 participants. 8 will be tested using subjective measures (Phase A). If a signal of efficacy is detected the last 2 participants will be tested using additional objective PSG measurements (Phase B). Phase B will be a feasibility study and based on results PI will apply for external funding.

AIMS FOR PHASE A:

The Primary aim of our study is to evaluate the effectiveness of prazosin in bulimic patients experiencing distressing nightmares secondary to PTSD using subjective measures.

Hypothesis 1:

Prazosin is associated with decrease in nightmare frequency in bulimic patients

The secondary aim of our study is to assess changes in Cortisol levels in bulimic patients with PTSD before and after treatment with prazosin.

Hypothesis 2:

Prazosin use is associated with a decrease of cortisol levels.

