6.3 Waiver or alteration of authorization statements of agreement

7.0 Study Design and Procedures

7.1 Study Design

Study Design: We plan to conduct a 7 week prospective, double blind, placebo controlled crossover study. Each patient, in a randomized design will receive three weeks of prazosin and three weeks of placebo separated by 1 week washout period. A 1-week washout period is considered sufficient, given that the half-life of prazosin is 2-3 hours, and previous studies have demonstrated that the clinical effects of prazosin are eliminated within a week^{10, 11}. The subjects

will be blinded and the randomization list will be sent directly to the research pharmacy. Methylcellulose will be used as placebo.

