7.2.3 Weekly Visits

Symptoms will be reassessed and medication will be adjusted by 1-2 mg increments every 7 days based on clinical response and severity of night mares, to achieve maximum therapeutic benefit while monitoring adverse effects using side effects scale on weekly basis (psychiatrist will be using the scale at every visit). A phone contact by RA will be made on the morning after dose initiation and after each increment to monitor adverse events. The end point for capping the Prazosin dose will be 6 mg daily. The psychiatrist will administer adverse events rating scale and nightmare assessment using Sleep-50 Questionnaire at every psychopharmacologic

visit after initiation of medication in addition to the initial visit. Vital signs will be checked at each visit as well. The participants will have a total of 7 visits with the psychiatrist (1 for initial evaluation and 3 for the dose titration during each study arm). Research pharmacy and RA will determine and track the sequence and random allocation of the medication to ensure blind randomized trial. RA will also gather salivary samples from the patient at end of each study arm (5 diurnal samples for each arm) After 3 weeks on one treatment arm, a wash out period of 1 week will be given prior to starting the second study arm. The same sequence will be repeated for the second study arm and study questionnaires will be repeated on the last day of the washout period. Blood work will be drawn thrice, once at baseline and once at the end of each study arm. 5 Diurnal salivary samples will be collected thrice, once at baseline and once at the end of each study arm. All sets of cortisol level will be collected at the same time points as the baseline level to allow accurate comparisons. All Rating scales will be completed 4 times, once at baseline, once at end of wash out period and once at the end of each study arm. At the end of each study arm, any unused medication will be collected from the participant. Upon completion of the study, participants may want to continue taking the study medication if they experienced positive results. The PI will discuss with each participant if it is appropriate to continue taking the medication.

Study Procedures (PHASE B)

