8.3 Access to data and/or specimens

8.4 Procedures to release data or specimens

8.5 Process for returning results

9.0 Statistical Plan (Phase A)

9.1 Sample size determination

Statistical Plan & Sample size determination

Power Calculation: Our plan is to recruit 10 patients with Bulimia nervosa and PTSD in this trial. Here we show our power calculations for the Hypothesis 1 and 2 based on our best knowledge. It should be noted that we assume no carry-over therapeutic effect in the calculation (see **Study Design**).

We choose the CAPS distressing dream item as the primary measure of nightmare frequency. Based on previous studies in similar patient populations, we assume the baseline nightmare score equals to 6.5, regardless of the treatment period. We anticipate the mean (SD) nightmare score of 6.0 (1.5) after being administered placebo for 3 weeks, and the endpoint mean (SD) for after be treated with Prazosin would reduce to 3.5 (2.5). We assumed that the correlation between two scores for the same patient equals to 0.3. With a sample size of 10 patients, we will have 80% power to detect the treatment effect, at 2-sided alpha level of 0.05. Other scenarios are presented in the table below.

CAPS Nightmare score			Correlation coefficient	Power
Baseline	Placebo	Prazosin		
6.5	6.0 (1.5)	3.5 (2.5)	0.3	80%
6.5	6.0 (1.5)	3.5 (2.5)	0.4	85%
6.5	6.5 (1.5)	3.5 (2.5)	0.3	92%
6.5	6.5 (1.5)	3.5 (2.5)	0.4	95%
6.5	6.5 (1.5)	4.0 (2.5)	0.3	81%
6.5	6.5 (1.5)	4.0 (2.5)	0.4	85%

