9.2 Statistical methods

Statistical methods

The initial analyses of the data will include univariate exploration of all variables, using histograms, statistical summaries, and other graphical techniques. Expected ranges for all of the variables will be defined a priori, and out of range values, or values identified as outliers will be checked for errors, including going back to the original data forms. In addition to data cleaning, this initial analysis will serve the purpose of describing the patients' characteristics.

Our main objective is to identify the treatment effect. We hypothesize that there will be a reduction in cortisol levels and other subjective scores after being treated with Prazosin, whereas no significant change after being administered with placebo. To examine the treatment effect, both univariate and multivariable methods will be used. The analytic plan for hypothesis 1 and 2 will be similar, except the outcome measurements.

Univariate: T-tests will be used to analysis the mean difference of nightmare score, cortisol level, and other subjective scores.

Multivariable regression model: The mixed effects model will be used to examine the differences of the objective measures and subjective scores between two treatment arms. In these models, we will account for the period effect (period 1 or 2) and sequence effect (sequence Placebo-Prazosin or Prazosin-Placebo). The sequence effect will be treated as a random effect. Demographic characteristics and baseline measures will be treated as confounders and adjusted in the models as well. We expect no significant differences in the outcome variables will be observed between baseline and placebo. Therefore, the analysis will focus on the Prazosin vs. Placebo. Least squares mean, standard error of the mean, and p value for the differences will be presented as the final results.

Statistical Plan (Phase B)

Protocol B is only a feasibility study using 2 subjects therefore statistical support is not required.

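### The plan does not require the two treatment orders to be balanced; if the list is unrestricted, the 8-patient crossover loses about 6 points of period-adjusted power on average, which a one-sentence blocking rule would avoid

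*Combined protocol and SAP*

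**What the plan says.** Section 24.1.3 explains what is randomised: "The randomization process will determine which subjects receive prazosin first and which subjects will receive placebo first". The method is given in one further sentence: "We will use computer generated random numbers for randomization process".

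Two other places touch on the list. Section 7.1 says that "the randomization list will be sent directly to the research pharmacy". Section 7.2.3 gives the research assistant a part in it as well: "Research pharmacy and RA will determine and track the sequence and random allocation of the medication". Neither gives a block size, a sequence ratio or a balancing rule. Section 16.0 allows for patients who withdraw after consent, without saying which treatment order their replacements take.

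On analysis, section 9.2 plans t-tests with no stated period adjustment, and a mixed model of which it says: "In these models, we will account for the period effect (period 1 or 2) and sequence effect". Section 9.1 states the power: "With a sample size of 10 patients, we will have 80% power to detect the treatment effect, at 2-sided alpha level of 0.05". Section 1.1 puts 8 of the 10 patients in Phase A and 2 in Phase B.

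**The concern.** In a two-period crossover, the treatment effect adjusted for period is estimated most precisely when the two sequences are equal in size. Precision falls as the split becomes uneven. If every patient has the same order, treatment cannot be separated from period.

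An analysis that ignores period has a different weakness. With unequal sequences, part of any drift between the first and second period is counted as treatment effect. In a large trial chance imbalance is minor. With 8 patients it need not be, and the decision to open Phase B rests on those 8. The protocol leaves the balance of its sequences unspecified, although fixing it would cost almost nothing.

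**Working it through.** **Inputs.** From section 9.1: placebo mean 6.0 (SD 1.5), prazosin mean 3.5 (SD 2.5), correlation 0.3, two-sided alpha 0.05, no carry-over. Assumed, because the documents do not say: each patient has probability 0.5 of either order, independently of the others.

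**Step 1: reproduce the plan's figure.** The difference is 6.0 − 3.5 = 2.5. The SD of the within-patient difference is √(1.5² + 2.5² − 2 × 0.3 × 1.5 × 2.5) = √6.25 = 2.5. A paired t-test with n = 10 and 9 df (noncentral t) gives 80.3%, against 80% stated. The plan's calculation is therefore a paired comparison with no period term. The same test with n = 8 gives 68.1%.

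**Step 2: how 8 patients split.** From Binomial(8, 0.5), with 256 equally likely lists: 4:4 in 70/256, 5:3 either way in 112/256, 6:2 in 56/256, 7:1 in 16/256 and 8:0 in 2/256. Then 6:2 or worse is 74/256 = 28.9%.

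**Step 3: period-adjusted power at each split.** Var = (SD²/4)(1/n₁ + 1/n₂) = 1.5625 × (1/n₁ + 1/n₂), with n − 2 = 6 df. Example at 6:2: 1.5625 × (1/6 + 1/2) = 1.042, SE 1.021, noncentrality 2.5/1.021 = 2.45. The last column is (n₁ − n₂)/n, the share of a period effect that enters an unadjusted paired t-test.

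| Split | Probability | Relative efficiency | Adjusted power | Share of period effect in paired t-test |
|---|---|---|---|---|
| 4:4 | 27.3% | 100% | 65.7% | 0 |
| 5:3 | 43.8% | 94% | 63.0% | 25% |
| 6:2 | 21.9% | 75% | 53.7% | 50% |
| 7:1 | 6.3% | 44% | 35.1% | 75% |
| 8:0 | 0.8% | 0 | not estimable | 100% |

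Weighting power by probability, with 8:0 counted as zero, gives 59.4%. The loss against 4:4 is 65.7 − 59.4 = 6.3 points.

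**Step 4: all 10 patients.** The same formulas with 8 df give 79.1% at 5:5, 77.4% at 6:4, 71.9% at 7:3 and 60.3% at 8:2. The average is 74.1%, a loss of 79.1 − 74.1 = 5.0 points.

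**Step 5: the t-test under assumed period effects (n = 8, simulated).** The documents give no period effect, so the range 0 to 1 point on the nightmare score is an illustration.

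- No period effect: power is about 68% at every split and there is no bias.
- 0.5 point at 6:2: bias 0.25 point, type I error 5.4%, and power 75% or 58% depending on which sequence is larger.
- 1 point: bias 0.25, 0.50 and 0.75 point at 5:3, 6:2 and 7:1, with type I error 4.3%, 6.3% and 10.1%. At 6:2 power is 79% or 45%, against 62% at 4:4.

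Averaged over all unrestricted lists, type I error stays at about 5%. The distortion is conditional on the split that occurs.

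The calculation includes treatment and period only. The demographic and baseline covariates in section 9.2 are left out.

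**The case against.** The strongest reply is that the protocol never says the list is unrestricted. Permuted blocks are also produced from computer-generated random numbers, and a list prepared in advance for the pharmacy is compatible with blocking. This stands. A reader might infer simple randomisation from section 24.1.3, but the text supports only the statement that no balance rule is specified. Every probability above is conditional on an unrestricted list.

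The usual cost is also modest. A 4:4 or 5:3 split occurs in 182/256 = 71% of lists, and 5:3 costs under 3 points. This stands too: the material loss begins at 6:2.

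A reader might infer that the trial's treatment estimate will be biased by period. The documents do not support that. The mixed model includes period, and section 9.2 presents least squares means as the final results. Only the t-tests are exposed, only if a period effect exists, and only conditionally on the split.

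A reader might also attribute the whole gap between the stated 80% and 59.4% to imbalance. Most of it has other causes: 80.3% to 68.1% comes from 8 patients instead of 10, and 68.1% to 65.7% from adding the period term. Only the last step, to 59.4%, is imbalance.

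Finally, two Phase B patients would share an order half the time (2 × 0.5 × 0.5). That carries little weight, since section 9.2 calls Phase B a feasibility study without statistical support.

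What remains is that nothing in the protocol guarantees balance, and this trial will have a single split with too few patients to absorb a poor one.

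**Conclusion.** The point holds as a cheap improvement to an underspecified design feature. It does not show that the planned analysis is invalid.

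As written, section 24.1.3 permits an unrestricted list. Under that reading, the expected cost is about 6 points of period-adjusted power for 8 patients, or 5 points for 10. For Phase A there is a 29% chance of a split that costs 12 points or more (65.7 − 53.7 = 12.0 at 6:2). The t-test exposure is a secondary reason for balance, because its size depends on a period effect that the documents do not give.

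These figures rest on the plan's means, SDs and correlation, on 1:1 allocation, and on a model with treatment and period only. If the list is already blocked, the power loss does not arise and a sentence saying so is enough. The rule for replacements and the access question in section 7.2.3 would still need an answer.

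**What to change.** 1. In section 24.1.3, state that sequence is allocated 1:1 by permuted blocks, giving 4:4 in Phase A.
2. State that a replacement is assigned to the withdrawn patient's sequence, with the assignment made by the pharmacy.
3. Optionally, put one Phase B patient in each sequence, which makes the total 5:5. This is not essential in a feasibility phase.
4. Bring section 7.2.3 into line with section 7.1, so that only the research pharmacy holds the list and the block details. The research assistant obtains consent (section 4.2) and collects the rating scales (section 7.2.2), and should not determine or track the sequence.

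The cost is a few sentences and, if the present list is unblocked, a regenerated one. The downside is that anyone who knows the earlier assignments and the block structure can work out the last ones; with one patient per sequence in Phase B, the first order reveals the second. That risk is small if item 4 is adopted. It cannot be called negligible while the research assistant shares control of the sequence.

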24.1.4 Subject Compliance Monitoring

Subjects will be seen by the psychiatrist each week during the study duration and will be asked to bring along their pill bottle so any remaining capsules can be counted and collected. The research assistant will also call the participants after each dosage increase to inquire about usage and side effects.

24.1.5 Blinding of the Test Article

The research pharmacy will provide the drug capsules which will be over encapsulated to maintain the same size as the capsules containing placebo.

24.1.6 Receiving, Storage, Dispensing and Return

24.1.6.1 Receipt of Test Article

We will obtain the drug and placebo from the Research Pharmacy.

24.1.6.2 Storage

The Research Pharmacy will store the drug and placebo according to their standard practice.

24.1.6.3 Preparation and Dispensing

Both the medication and placebo will be prepared by the Research Pharmacist experienced in drug research studies. The drug capsules will contain 1 mg prazosin and will be over encapsulated. Methylcellulose will be used in the placebo capsules.

24.1.6.4 Return or Destruction of the Test Article

At the conclusion of each study arm, the participant will return their pill bottle, so that any remaining capsules can be counted and collected and will be destroyed on site.

24.1.6.5 Prior and Concomitant Therapy

Prazosin is the only treatment being offered in this study. Subjects cannot be taking steroids or beta blockers and will be excluded from the study if used.
